5. STATISTICAL ANALYSES

5.1 GENERAL CONSIDERATION

All virology and efficacy analyses will be performed on the mITTi population.

All primary and secondary virology endpoints will be produced using the nasopharyngeal swab samples. Additional descriptive analyses for saliva and serum samples will be performed on an exploratory basis for the primary and secondary virology endpoints, as required. A summary of the sampling differences between cohorts is provided in [Table 3](#). Refer to Appendix 1 and Appendix 2 of the study protocol for further details.

No alpha adjustments for multiple comparisons are planned.

For all cohorts, the primary virology analysis will be performed as part of a Day 10 Review (accompanied with key safety review if deemed necessary, see [Section 5.7.1](#)) which is to be completed after all patients enrolled in the current cohort have completed assessments through Day 10. Other endpoints will be analyzed at the completion of each full cohort or at the completion of the study. All analyses at the Day 10 review or at the completion of each cohort will compare each AT-527 dose group and a combined placebo group, including all placebo patients enrolled across cohorts up to the cohort being analyzed, while analyses performed at the completion of the study will compare each AT-527 dose group and a combined placebo group from all cohorts.

Table 3 Differences in Virology Sampling Between Cohorts

Assessment	Cohort A	Cohorts B–E
Nasopharyngeal swab sample for COVID-19 virology	Once a day on Days 1, 3, 5, and 7	Once a day on Days 1, 3, 5, and 7
Saliva sample for COVID-19 virology	NA	Once a day on Days 1, 3, 5, and 7
Serum sample for anti-SARS-CoV-2 antibodies and viral RNA	Once a day on Days 1 and 7	Once a day on Days 1, 3, 5, and 7

COVID-19 = coronavirus disease 2019; NA = not applicable; SARS-CoV-2 = severe acute respiratory syndrome coronavirus-2.

For virology endpoints, the time windows for each assessment are given in [Table 4](#). The time windows will be used for all virology endpoints except the time-to-event endpoints.

Table 4 Virology Assessment Time Windows

Scheduled Timepoint ^{a, b, d}	Acceptable Time Window
Baseline (Day 1 pre-dose)	Day 1 pre-dose ^c
Day 3	Day 2 – Day 3
Day 5	Day 4 – Day 5
Day 7	Day 6 – Day 8

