Baseline (Day 1 pre-dose)	Day 1 pre-dose ^b
Day 3	Day 2 – Day 4
Day 7	Day 5 – Day 9

^a An unscheduled visit represents a visit that is not specified by the protocol but is determined to be necessary by the investigator or Sponsor (e.g., for evaluation of an adverse event).

Assessments (including PK sample collection) should be performed as clinically indicated.

For unscheduled visits occurring after Day 7, PK sample collection is not required.

^b Baseline is defined as the last assessment prior to treatment.

Unscheduled visit and early termination visit data will also be mapped according to the acceptable time windows per [Table 4](#), [Table 5](#), and [Table 6](#). Where multiple measurements within a visit window are available for a patient, the value obtained closest to the target timepoint (center of the acceptable time window) will be used. If two measurements collected with the same time deviation exist before and after the target timepoint, the measurement obtained before the target timepoint will be adopted for analysis. However, preference will always be given to measurements collected on the day specified in the scheduled timepoint. The assessment timepoint having no

measurements within the corresponding acceptable time window will be considered as missing and will not be included in the analysis for the timepoint in question.

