5.3.2 Main Analytical Approach for Primary Virology Endpoint

The primary virology endpoint analyses will be performed on the mITTi population using the nasopharyngeal swab data.

For each cohort, the change from baseline in the amount of SARS-CoV-2 virus RNA will be compared between the AT-527 group and the pooled placebo group (meaning all placebo patients up to and including the cohort being analyzed will be used to form the placebo comparator group) at Days 3, 5, and 7 using analysis of covariance (ANCOVA) with baseline viral load as a covariate.

The least squares mean (LSM) change and its standard error (SE) of means in each group, the difference between two groups in LSM change, SE, and 80% CI, and p-values will be presented. The LSM change will be presented graphically over time.

Additionally, descriptive summaries for the change from baseline will also be presented by treatment group. The change from baseline and the amount of SARS-CoV-2 virus RNA will also be presented graphically over time.

Baseline is defined as the Day 1 (pre-dose) nasopharyngeal swab ([Table 4](#)).

If the data are not normally distributed, a non-parametric alternative method will be used (e.g., Mann-Whitney U test) to compare distributions.

The qualitative result of the SARS-CoV-2 RT-PCR test is determined using cycle threshold (Ct) values. If the qualitative result is positive, then an associated quantitative result is also provided. The quantitative result is either numerical or below the limit of quantification (BLQ). The limit of quantification (LOQ) for the virus RNA is 120 copies/ml. If the virus RNA sample has a positive qualitative result, but a quantitative result BLQ, virus RNA will be imputed as LOQ – 1 (119 copies/mL). Negative qualitative samples will be imputed as LOQ/2 (60 copies/ml) before being transformed to the log10 scale. Samples reported as positive, but not quantifiable, will contribute to qualitative summaries, but will be treated as missing (not imputed) for quantitative summaries.

Missing data will not be imputed. Any missing data will not be included in the analyses.

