5.3.3 Sensitivity Analyses for Primary Virology Endpoint

A sensitivity analysis may be performed, whereby only data obtained at the nominal timepoint is used. This means that the time windows in [Table 4](#) would not be applicable; only samples collected on the scheduled timepoints (Days 3, 5, and 7) would be included in the analysis.

At the end of the study, sensitivity analyses will also be performed for each cohort with a combined placebo group from all cohorts.

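### Virology windows at Days 3 and 5 have no late day, so swabs taken one day late are lost to the primary analysis or, rarely, used at the wrong visit (minor)

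*SAP*

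**What the plan says.** SAP Section 5.1, Table 4 gives the virology windows: Days 2–3 for Day 3, Days 4–5 for Day 5 and Days 6–8 for Day 7. They govern the primary endpoint: "The time windows will be used for all virology endpoints except the time-to-event endpoints".

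The text after Table 6 sets the rules within a window:

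- With several values, "the value obtained closest to the target timepoint (center of the acceptable time window) will be used".
- On a tie, the earlier value wins: "If two measurements collected with the same time deviation exist before and after the target timepoint, the measurement obtained before the target timepoint" is adopted.
- Both rules yield to the scheduled day: "preference will always be given to measurements collected on the day specified in the scheduled timepoint".
- A timepoint without "measurements within the corresponding acceptable time window will be considered as missing".

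SAP Section 5.3.2 then says of the primary analysis: "Missing data will not be imputed. Any missing data will not be included in the analyses". SAP Section 5.3.3 adds an optional check: "A sensitivity analysis may be performed, whereby only data obtained at the nominal timepoint is used".

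The protocol's schedules of activities (Appendices 1–3) place swabs on Days 3, 5 and 7 with no stated tolerance. They do give one for Day 14 (±2 days) and Day 33 (±3 days).

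**The concern.** The windows are lopsided. Day 7 accepts a swab one day early or one day late; Days 3 and 5 accept only the early one. A swab that is one day late at Day 3 or Day 5 falls into the next visit's window. There it competes with that visit's own swab, and its own visit is left without a value.

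The primary endpoint is change from baseline at exactly these three days, and protocol Section 3.3.3 expects viral load to fall from visit to visit. Two things are at stake. Patients who were swabbed can drop out of the Day 3 or Day 5 comparison. In some patterns, a value is analysed under the label of a visit it does not belong to. The sample size allows only for a 90% positive rate (SAP Section 3), not for swabs lost in this way.

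**Working it through.** **What the rules do to particular patterns.** Each row gives the actual days of the Day 3, Day 5 and Day 7 visits, with deviation counted in whole days.

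| Actual days | Analysed as Day 3 | Analysed as Day 5 | Analysed as Day 7 | Swab dropped |
|---|---|---|---|---|
| 4, 5, 7 | missing | Day 5 visit | Day 7 visit | Day 4 |
| 3, 6, 7 | Day 3 visit | missing | Day 7 visit | Day 6 |
| 3, 6, 8 | Day 3 visit | missing | Day 5 visit | Day 8 |
| 4, 6, 7 | missing | Day 3 visit | Day 7 visit | Day 6 |
| 4, 6, 8 | missing | Day 3 visit | Day 5 visit | Day 8 |
| 3, 5, 8 | Day 3 visit | Day 5 visit | Day 7 visit | none |

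In the second and fourth rows the scheduled-day preference protects the swab taken on Day 7. In the third and fifth rows, Days 6 and 8 are each one day from Day 7 and the tie goes to Day 6.

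**All patterns within one day.** Each visit can be early, on time or late, which gives 3 × 3 × 3 = 27 patterns. Six put two visits on the same day, leaving 21. Of these, 9 lose a collected swab and leave a timepoint empty, and 4 of those 9 also use another visit's swab.

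**How often.** The documents give no lateness rate. Assume each visit is independently one day late with probability q and never early. Then:

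- Day 3 missing = q (the Day 3 visit is late).
- Day 5 missing = q(1 − q) (the Day 5 visit is late and the Day 3 visit is not).
- Wrong visit at Day 5 = q² (Day 3 and Day 5 visits both late).
- Wrong visit at Day 7 = q² (Day 5 and Day 7 visits both late).
- Any collected swab lost = 1 − (1 − q)².
- Day 7 is never missing.

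| q | Day 3 missing | Day 5 missing | Wrong visit, Day 5 and Day 7 each | Any swab lost |
|---|---|---|---|---|
| 2% | 2% | 2.0% | 0.04% | 4.0% |
| 5% | 5% | 4.8% | 0.25% | 9.8% |
| 10% | 10% | 9.0% | 1.0% | 19.0% |

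**Power.** First, the SAP's own figure (Section 3: 0.7 log10 with SD 1.2, one-sided 10%, 80% power). By the normal approximation:

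n = 2 × 1.2² × (1.2816 + 0.8416)² / 0.7² = 26.5, rounded up to 27 per group, and 27 / 0.9 = 30. The SAP's figures are reproduced.

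Power = Φ(0.7 / (1.2 × √(2/n)) − 1.2816), with n reduced to 27(1 − q) at Day 3:

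| q | n per group | Power at Day 3 |
|---|---|---|
| 0 | 27 | 0.806 |
| 2% | 26.46 | 0.800 |
| 5% | 25.65 | 0.790 |
| 10% | 24.3 | 0.774 |

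Protocol Section 6.1 sizes Cohort E at 100 per arm (0.5 log10, SD 1.25, one-sided 2.5%). If the same windows were carried over to it, power by the same method would go from 0.807 to 0.800, 0.787 and 0.765.

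**The case against.** Three stronger readings are tempting, and the documents do not support them.

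First, a reader of the tie rule alone might infer that a late Day 5 swab can replace a proper Day 7 swab. The scheduled-day preference comes directly after it and rules this out for any swab taken on Day 7. Replacement needs the Day 5 visit on Day 6 and the Day 7 visit on Day 8. Even then the SAP does not say whether deviation is counted in days or hours; in hours, the Day 8 swab could win.

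Second, a reader might infer a material bias in the treatment effect. At q = 10%, 1% of Day 5 values and 1% of Day 7 values come from another visit. At an assumed decline of 0.5 log10 per day, that moves an arm mean by 0.01 × 0.5 = 0.005 log10. Arms are randomized and blinded, so most of this should cancel.

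Third, Table 6 maps Days 2–4 to Day 3 for laboratory tests, which might look like a contradiction. Laboratory samples have no Day 5 draw, so Day 4 is not contested. The closer match is Table 5: vital signs are also taken on Days 3, 5 and 7 and use exactly the Table 4 windows. Non-overlapping windows are a recognizable choice.

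Two more points stand. Mobile nursing and optional confinement on Days 1–7 (protocol Section 3.1) favour punctual visits, so q may be small. The choice is also partly between missing and mistimed values: a Day 4 swab kept at Day 3 is itself a day off. Under the fix at q = 10%, off-day values rise from 0% to 10% at Day 3 and from 1% to 10% at Day 5, and stay at 10% at Day 7.

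The objection does not explain why a one-day-late swab is acceptable at Day 7 and a one-day-early swab at every visit, but a late one at Day 3 or Day 5 is not. Nor does the nominal-day analysis help with the loss: "only samples collected on the scheduled timepoints (Days 3, 5, and 7) would be included in the analysis", so it removes wrong-visit values but discards the late swabs as well.

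**Conclusion.** The point holds as a minor one. By the SAP's text alone, a Day 3 visit on Day 4 always empties Day 3, and a Day 5 visit on Day 6 empties Day 5 unless a Day 4 swab exists. The swab was collected in both cases, and nothing else in the plan recovers it for its own visit.

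The harm is chiefly lost data at Days 3 and 5. Wrong-visit values need two late visits, or one late and one missed, and are rare if lateness is independent between visits. If lateness instead persisted fully within patients, a share q would follow the Days 4, 6, 8 pattern: Day 3 missing and wrong-visit values at both Day 5 and Day 7, but no loss at Day 5.

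All rates and power losses rest on the assumed q of 2% to 10%. The power figures are two-sample approximations, as in the SAP's sample size section, whereas the analysis is an ANCOVA adjusting for baseline. They show the order of size: roughly 1 to 3 percentage points of power at Day 3, and no patients lost at Day 7.

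**What to change.** In SAP Section 5.1, assign a scheduled swab to its own visit, by visit label, when it is taken within one day either side of target: Days 2–4 for Day 3, Days 4–6 for Day 5 and Days 6–8 for Day 7. Break ties in favour of the scheduled visit's swab, and state whether deviation is counted in days or hours.

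Use the existing non-overlapping Table 4 windows only to place unscheduled or early termination swabs when the scheduled visit's swab is missing. Days 4 and 6 then stay unambiguous. Reword the scheduled-day preference so that its order relative to these rules is clear. Keep the nominal-day analysis as a sensitivity check.

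With this change, none of the 21 patterns above loses a swab or uses one from another visit. The cost is a change of wording and one derivation rule, best made before unblinding, with no new data. The drawback is that some Day 3 and Day 5 values will be one day late instead of missing.

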5.3.5.9 Lack of Efficacy or Worsening of COVID-19

Medical occurrences or symptoms of deterioration that are anticipated as part of COVID-19, such as fluctuations in symptoms, should not be recorded as adverse events. However, deterioration that is judged by the investigator to have unexpectedly worsened in severity or frequency or changed in nature at any time during the study should be recorded as an adverse event. When recording an unanticipated worsening of COVID-19 on the Adverse Event eCRF, it is important to convey the concept that the condition has changed by including applicable descriptors (e.g., "accelerated worsening of coronavirus disease 2019").

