Appendix 1: Schedule of Activities for Cohort A

COVID-19=coronavirus disease 2019; ET=early termination; PK=pharmacokinetic; RT-PCR=reverse-transcription polymerase chain reaction; SARS-CoV-2=severe acute respiratory syndrome coronavirus-2; PRO=patient-reported outcome; UV=unscheduled visit.

Notes: On treatment days (Days 1–5), all assessments should be performed prior to dosing, unless otherwise specified.

- ^a Screening assessments may be performed up to 72 hours prior to Day 1 or on Day 1.
- ^b An unscheduled visit represents a visit that is not specified by the protocol but is determined to be necessary by the investigator or Sponsor (e.g., for evaluation of an adverse event). Assessments (including PK sample collection) should be performed as clinically indicated. For unscheduled visits occurring after Day 7, PK sample collection is not required.
- ^c Patients who discontinue study drug prematurely will continue to complete assessments as indicated until the end of the study. Patients who discontinue from study participation will have an early termination visit 7 (± 2) days after their final dose of study drug. Patients who discontinue from the study after Day 14 will not be required to complete an early termination visit.
- ^d Required follow-up information will be collected via telephone call at Day 14 (± 2 days) and Day 33 (± 3 days).
- ^e Informed consent must be documented before any study-specific screening procedure is performed.
- ^f For patients at participating sites who have provided written or electronic informed consent to participate in mobile nursing visits, this assessment or procedure may be performed by a trained nursing professional at the patient's home.
- ^g COVID-19 Symptom Diary includes questions regarding symptoms (Items 1–14) and the Patient Global Impression of Severity. On assessment visit days, questionnaires will be self-administered before the patient receives any information on disease status, prior to the performance of non-PRO assessments, and prior to the administration of study treatment. On Day 1, the first diary questionnaire should be completed prior to the first dose. On Days 1–14, the questionnaire (including recording of temperature) should be completed twice a day (morning and evening) at the same time each day.
- ^h On Days 15–28, the questionnaire (including recording of temperature) should be completed once a day in the evening at the same time each day.

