^a An unscheduled visit represents a visit that is not specified by the protocol but is determined to be necessary by the investigator or Sponsor (e.g., for evaluation of an adverse event). Assessments (including PK sample collection) should be performed as clinically indicated. For unscheduled visits occurring after Day 7, PK sample collection is not required.

^b Patients who discontinue study drug prematurely will continue to complete assessments as indicated until the end of the study. Patients who discontinue from study participation will have an early termination visit 7 (\pm 2) days after their final dose of study drug. Patients who discontinue from the study after Day 14 will not be required to complete an early termination visit.

^c If no pre-dose sample is available, a sample taken up to 2 hours post-dose can be used as baseline.

^d No unscheduled visit or early termination serum sample to be taken for Cohort A.

For vital signs, including oxygen saturation, the time windows for each assessment are given in [Table 5](#).

Table 5 Vital Signs (Including Oxygen Saturation) Time Windows

Scheduled Timepoint ^{a, b, d}	Acceptable Time Window
Baseline (Day 1 pre-dose)	Day 1 pre-dose ^c
Day 3	Day 2 – Day 3
Day 5	Day 4 – Day 5
Day 7	Day 6 – Day 8

^a An unscheduled visit represents a visit that is not specified by the protocol but is determined to be necessary by the investigator or Sponsor (e.g., for evaluation of an adverse event).

Assessments (including PK sample collection) should be performed as clinically indicated.

For unscheduled visits occurring after Day 7, PK sample collection is not required.

^b Patients who discontinue study drug prematurely will continue to complete assessments as indicated until the end of the study. Patients who discontinue from study participation will have an early termination visit 7 (± 2) days after their final dose of study drug. Patients who discontinue from the study after Day 14 will not be required to complete an early termination visit.

^c Baseline is defined as the last assessment prior to treatment.

^d These time windows do not apply to temperature. Temperature is collected as part of the COVID-19 Symptom Diary (twice a day on Days 1–14; once a day on Days 15–28).

For lab parameters (hematology, chemistry), the time windows for each assessment are given in [Table 6](#).

Table 6 Laboratory (Hematology, Chemistry) Time Windows

Scheduled Timepoint ^a	Acceptable Time Window

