- AEs of NCI CTCAE Grade 3 or higher
- AEs by most extreme NCI CTCAE grade
- AEs and SAEs by outcome
- AEs and SAEs by time of onset according to the following categories:
 - Week 1 (Days 1-7)
 - Week 2 (Days 8-14)
 - Days ≥ 15

All adverse events of special interest (AESI) will be presented by treatment group. AESI are as follows for this study:

- Cases of potential drug-induced liver injury that include an elevated alanine transaminase (ALT) or aspartate aminotransferase (AST) in combination with either an elevated bilirubin or clinical jaundice, as defined by Hy's Law (as detailed in protocol)
- Suspected transmission of an infectious agent by the study drug, as defined below Any organism, virus, or infectious particle (e.g., prion protein transmitting transmissible spongiform encephalopathy), pathogenic or non-pathogenic, is considered an infectious agent. A transmission of an infectious agent may be suspected from clinical symptoms or laboratory findings that indicate an infection in a patient exposed to a medicinal product. This term applies only when a contamination of the study drug is suspected.

Details of any deaths will be presented in the form of an individual patient listing, as well as in a frequency table by treatment group.

- **Change from baseline in targeted vital signs, including peripheral capillary oxygen saturation (SpO₂)**

For each of the vital signs (pulse rate, respiratory rate, blood pressure, peripheral capillary oxygen saturation [SpO₂], and temperature), summary statistics on absolute value and the change from baseline will be presented over time. For all cohorts, this will be presented by treatment group at all timepoints using a combined placebo group containing patients from all cohorts.

Additionally, for all cohorts, a graphical representation of means over time of temperature (daily to Day 28) will be presented. Summaries of other temperature related secondary efficacy endpoint are described in Section 5.4.2.3.

Baseline is defined as the last assessment prior to treatment.

- **Change from baseline in targeted clinical laboratory test results**

For each of the hematological and biochemical test parameters, summary statistics of observed and change from baseline values at each timepoint will be presented by treatment group for each scheduled timepoint. Baseline is defined as the last assessment prior to treatment.

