Additionally, shift tables of selected laboratory tests will be used to summarize the baseline and maximum post-baseline severity grade. NCI CTCAE v5.0 grading will be used with an indication of the direction of the abnormality (High, Low). A summary of the number and percentage of patients with abnormal laboratory outcomes will be produced by treatment group and pooled placebo group for each parameter for each scheduled timepoint.

The number and proportion of patients who meet the pre-specified criteria shown in [Table 8](#) will be presented by treatment group during the study.

Table 8 Pre-specified Treatment-Emergent Abnormal Laboratory Criteria

AST (U/L) or ALT (U/L) and Total bilirubin (mg/dL)
AST (U/L) or ALT (U/L) > 3 × Baseline
AST (U/L) or ALT (U/L) > 5 × Baseline
AST (U/L) or ALT (U/L) > 3 × Baseline and Total bilirubin (mg/dL) > 2 × ULN

ALT= alanine aminotransferase; AST= aspartate aminotransferase; ULN= upper limit of normal.

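### Vital signs from unscheduled visits are usually left out of the by-visit summary and no worst-value table picks them up, so a transient fall in SpO2 shows only if reported as an adverse event or complication

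*SAP*

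**What the plan says.** Protocol Section 2 and SAP Table 1 list change from baseline in targeted vital signs, including SpO2, as a secondary safety endpoint. SAP 5.4.2.2 states the output: for each vital sign, "summary statistics on absolute value and the change from baseline will be presented over time". The same section gives laboratory tests more: "shift tables of selected laboratory tests will be used to summarize the baseline and maximum post-baseline severity grade", counts of abnormal results, and the Table 8 criteria.

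SAP 5.1 decides which readings enter a by-visit table. "For vital signs, including oxygen saturation, the time windows for each assessment are given in" Table 5: Days 2–3 for Day 3, Days 4–5 for Day 5, Days 6–8 for Day 7. "Unscheduled visit and early termination visit data will also be mapped according to the acceptable time windows per" Tables 4 to 6. If a window holds several readings, "the value obtained closest to the target timepoint (center of the acceptable time window) will be used", followed by the override: "However, preference will always be given to measurements collected on the day specified in the scheduled timepoint". Table 5 footnote d exempts temperature.

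The schedules in Protocol Appendices 1–3 include vital signs at unscheduled and early-termination visits. An unscheduled visit is one "determined to be necessary by the investigator or Sponsor (e.g., for evaluation of an adverse event"). Appendix 3 also schedules vital signs for Cohort E on Day 14.

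**The concern.** Unscheduled visits tend to happen when something has gone wrong, so their readings are more likely than scheduled ones to be abnormal. Under the rule, a patient who attends the scheduled visits will rarely have such a reading summarised. A worst-value table would recover it, but none is planned for vital signs.

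At stake is whether a difference between AT-527 and placebo in short-lived desaturation can be seen in the endpoint meant to show it. In its place the reader must rely on adverse-event reporting. Protocol 5.3.5.9 limits that, because "symptoms of deterioration that are anticipated as part of COVID-19" are not to be recorded as adverse events. In this disease, whether a fall in SpO2 was anticipated is a judgement for the investigator.

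**Working it through.** The plan states no figure to reproduce. The check applies the SAP 5.1 rule to Table 5 and then compares the planned outputs.

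**1. One unscheduled non-temperature reading, placed on each day from 2 to 33**

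| Day of reading | Scheduled visit in that window attended | Scheduled visit in that window missed |
|---|---|---|
| 2, 4, 6, 8 | Not used: the Day 3, 5 or 7 value wins | Used |
| 3, 5, 7 | Both readings are on the scheduled day; selection depends on clock time relative to the window centre | Used |
| 9–33 | No window | No window |

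Days 2–33 are 32 days and Table 5 covers 7 of them, so 32 − 7 = 25 have no window. This counts days, not readings. Day 1 post-dose also has no window.

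**2. Early termination**

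The visit falls 7 (±2) days after the final dose (Protocol 4.6.2). With the final dose on Day d, it falls on Days d + 5 to d + 9.

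| Final dose | Early-termination days | Days inside Table 5 |
|---|---|---|
| Day 1 | 6–10 | 6, 7, 8 |
| Day 2 | 7–11 | 7, 8 |
| Day 3 | 8–12 | 8 |
| Day 4 | 9–13 | none |
| Day 5 | 10–14 | none |
| Day 6 (late first dose) | 11–15 | none |

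Only 3 + 2 + 1 = 6 of the 6 × 5 = 30 combinations fall in a window. After a final dose on Day 4 or later, none does.

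**3. Cohort E, Day 14**

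The reading is scheduled in Protocol Appendix 3 but has no row in SAP Table 5. Cohort E is 224 of about 404 planned patients: 224/404 = 55%.

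**4. Outputs compared (SAP 5.4.2.2)**

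| Output | Selected laboratory tests | Vital signs |
|---|---|---|
| Absolute value and change by timepoint | Yes | Yes |
| Maximum post-baseline grade | Yes | No |
| Count of patients abnormal or past a threshold | Yes | No |

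**5. Illustration**

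The documents give no SpO2 data and no rate of unscheduled visits, so every value here is assumed. Suppose k of n patients have a fall at an unscheduled visit outside the scheduled days, have recovered at scheduled visits, and have no adverse event or complication recorded. The planned by-visit mean then moves by 0. Using each patient's minimum instead, the mean shift is −(fall × k/n) and the share affected is k/n. The n of 30 is one active arm in Cohorts A–D (60 × 1/2, or 40 × 3/4); 112 is one arm of Cohort E.

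| Fall | k/n | Shift in mean minimum | Share in a count |
|---|---|---|---|
| 97% to 90% | 2/30 | −7 × 2/30 = −0.47 | 6.7% |
| 96% to 90% | 1/30 | −6 × 1/30 = −0.20 | 3.3% |
| 96% to 90% | 3/30 | −6 × 3/30 = −0.60 | 10% |
| 96% to 90% | 5/112 | −6 × 5/112 = −0.27 | 4.5% |

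Even with the readings retained, the mean moves by well under one point. The count shows the event; the mean does not.

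**The case against.** A reader might infer that unscheduled vital signs are thrown away and that a fall in SpO2 never reaches any safety result. The documents support neither reading. The values are mapped, and are used on Days 2–8 when the scheduled-day value is missing. A reading taken on Day 3, 5 or 7 can itself be selected. Temperature is outside the windows and is plotted daily to Day 28.

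There is also a real alternative route. Protocol 4.5.4 sends clinically significant new or worsened vital-sign abnormalities to the Adverse Event eCRF. Protocol 5.3.5.5 makes reporting mandatory if the abnormality is symptomatic, changes study treatment, leads to intervention or a change in concomitant therapy, or is clinically significant. SAP 5.4.2.2 tabulates adverse events by grade and time of onset, and SAP 5.4.2.3 counts hospitalization, pneumonia and acute respiratory failure as complications. Protocol 5.3.5.9 itself requires unexpected worsening to be recorded. A fall to 90%, below the 93% that Protocol 4.1.2 lists as a sign of illness requiring hospitalization, is among the cases most likely to be reported.

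This all stands, and it makes the alternative route partial rather than absent. What it leaves out is a fall judged to be anticipated COVID-19 deterioration that does not become a listed complication. The Medical Monitor's review of vital-sign abnormalities (Protocol 3.1) is oversight, not a reported comparison between arms. The key safety outputs for the Day 10 review and the Cohort A interim (SAP 5.7.1 and 5.8.1) do not list vital signs. Protocol 6.5 plans vital-sign data by time with grades where appropriate, but no worst value.

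Two further objections also stand. Preferring the scheduled-day value keeps event-triggered readings out of scheduled-visit means, so calling those means biased towards no change is not supported: they describe change at scheduled visits. The missing Day 14 row has a different cause. The SAP still describes Cohort E as 40 patients randomized 3:1 with a Day 14 telephone call.

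**Conclusion.** The point holds as a reporting gap, not as an error in the window rule. For patients who attend Days 3, 5 and 7, non-temperature vital signs from unscheduled visits on other days do not enter the by-visit summary. No value after Day 8 has a window, which removes most early-termination readings and all Cohort E Day 14 readings. No worst-value or threshold summary for vital signs compensates.

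The size cannot be estimated from the documents. The 2/30 example shows only how the outputs would differ, and holds only if no adverse event or complication was recorded for those patients. The analysis is descriptive and other routes exist, so this does not threaten the trial's main conclusions. It is a worthwhile, inexpensive improvement, because by-visit means cannot show infrequent desaturation even when every reading is kept.

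**What to change.** In SAP 5.4.2.2, add one table by treatment group of each patient's worst post-baseline value and its change from baseline: minimum SpO2, maximum pulse rate, maximum respiratory rate, and minimum and maximum blood pressure. Use all scheduled, unscheduled and early-termination assessments after the first dose, whatever the window.

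In the same table, give the number and percentage of patients with SpO2 at or below 93%. Protocol 4.1.2 uses that level for room air, so flag readings taken on oxygen where this is known.

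Add a Day 14 row to Table 5 for Cohort E; Protocol Appendix 3 allows ±2 days for that visit. Leave the window rule unchanged for by-visit tables.

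The cost is SAP wording and one table from data already collected, and the SAP needs revision for Cohort E in any case. The downside is that a worst value depends on how many readings a patient has. Blinding does not remove this if one arm has more event-triggered visits, so show the number of readings per patient by arm alongside.
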